13.4 Demographic and Baseline Characteristics

Baseline characteristics will be assessed by the use of tables and/or graphs for each cohort separately. No statistical hypothesis tests will be performed on these characteristics. The number and percentage of subjects screened, the primary reasons for screening failure, and the primary reason for discontinuation will be displayed. Demographic variables (e.g., age, gender), baseline characteristics, primary and secondary diagnoses, and prior and concomitant therapies will be summarized by arm either by descriptive statistics or categorical tables.

APPENDIX A: KARNOFSKY PERFORMANCE STATUS (KPS) CRITERIA

Percent	Description
100	Normal, no complaints, no evidence of disease.
90	Able to carry on normal activity; minor signs or symptoms of disease.
80	Normal activity with effort; some signs or symptoms of disease.
70	Cares for self, unable to carry on normal activity or to do active work.
60	Requires occasional assistance, but is able to care for most of his/her needs.
50	Requires considerable assistance and frequent medical care.
40	Disabled, requires special care and assistance.
30	Severely disabled, hospitalization indicated. Death not imminent.
20	Very sick, hospitalization indicated. Death not imminent.
10	Moribund, fatal processes progressing rapidly.
0	Dead.

APPENDIX B: TABLE OF EIAEDS AND NON-EIAEDS*

CYP3A4 enzyme-inducing antiepileptic drugs	Non-CYP3A4 enzyme-inducing antiepileptic drugs
Carbamazepine Oxcarbazepine Phenytoin Fosphenytoin Phenobarbital Primidone	Levetiracetam Valproic acid Lacosamide Gabapentin Topiramate Lamotrigine Tiagabine Zonisamide Clonazepam Clonozam Pregabalin

* This is a partial list. A comprehensive list of EIAEDs can be found at The University of Indiana (<http://medicine.iupui.edu/clinpharm/ddis/>) has a comprehensive list of EIAEDs which should be consulted.

APPENDIX C: NEUROLOGIC ASSESSMENT IN NEURO-ONCOLOGY (NANO) SCALE

Scoring assessment is based on direct observation and testing performed during clinical evaluation and is not based on historical information or reported symptoms. Please check 1 answer per domain. Please check “Not assessed” if testing for that domain is not done. Please check “Not evaluable” if a given domain cannot be scored accurately due to pre-existing conditions, co-morbid events and/or concurrent medications.

Study #, Participant # and Initials: _____ / _____
 Date Assessment Performed (day/month/year): _____
 Study time point (i.e. cycle 1, day 1, etc): _____
 Assessment performed by (please print name): _____

Domains

Key Considerations

Gait

- 0 Normal
- 1 Abnormal but walks without assistance
- 2 Abnormal and requires assistance (companion, cane, walker, etc.)
- 3 Unable to walk
- Not assessed
- Not evaluable

- Walking is ideally assessed by at least 10 steps

Strength

- 0 Normal
- 1 Movement present but decreased against resistance
- 2 Movement present but none against resistance
- 3 No movement
- Not assessed
- Not evaluable

- Test each limb separately
- Recommend assess proximal (above knee or elbow) and distal (below knee or elbow) major muscle groups
- Score should reflect worst performing area
- Patients with baseline level 3 function in one major muscle group/limb can be scored based on assessment of other major muscle groups/limb

Ataxia (upper extremity)

- 0 Able to finger to nose touch without difficulty
- 1 Able to finger to nose touch but difficult
- 2 Unable to finger to nose touch
- Not assessed
- Not evaluable

- Non-evaluable if strength is compromised
- Trunk/lower extremities assessed by gait domain
- Particularly important for patients with brainstem and cerebellar tumors
- Score based on best response of at least 3

Sensation

- 0 Normal
- 1 Decreased but aware of sensory modality
- 2 Unaware of sensory modality
- Not assessed
- Not evaluable

- Recommend evaluating major body areas separately (face, limbs and trunk)
- Score should reflect worst performing area
- Sensory modality includes but not limited to light touch, pinprick, temperature and proprioception
- Patients with baseline level 2 function in one major body area can be scored based on

Study #, Participant # and Initials: _____ / _____
 Date Assessment Performed (day/month/year): _____
 Study time point (i.e. cycle 1, day 1, etc): _____

Visual Fields

- 0 Normal
- 1 Inconsistent or equivocal partial hemianopsia (≥quadrantopsia)
- 2 Consistent or unequivocal partial hemianopsia (≥quadrantopsia)
- 3 Complete hemianopsia
- Not assessed
- Not evaluable

- Patients who require corrective lenses should be evaluated while wearing corrective lenses
- Each eye should be evaluated and score should reflect the worst performing eye

Facial Strength

- 0 Normal
- 1 Mild/moderate weakness
- 2 Severe facial weakness
- Not assessed
- Not evaluable

- Particularly important for brainstem tumors
- Weakness includes nasolabial fold flattening, asymmetric smile and difficulty elevating

Language

- 0 Normal
- 1 Abnormal but easily conveys meaning to examiner
- 2 Abnormal and difficulty conveying meaning to examiner
- 3 Abnormal. If verbal, unable to convey meaning to examiner. OR non-verbal (mute/global aphasia)
- Not assessed
- Not evaluable

- Assess based on spoken speech. Non-verbal cues or writing should not be included.
- Level 1:** Includes word finding difficulty; few paraphasic errors/neologisms/word substitutions; but able to form sentences (full/broken)
- Level 2:** Includes inability to form sentences (<4 words per phrase/sentence); limited word output; fluent but “empty” speech.

Level of Consciousness

- 0 Normal
- 1 Drowsy (easily arousable)
- 2 Somnolent (difficult to arouse)
- 3 Unarousable/coma
- Not assessed
- Not evaluable

- None

Behavior

- 0 Normal
- 1 Mild/moderate alteration
- 2 Severe alteration
- Not assessed
- Not evaluable

- Particularly important for frontal lobe tumors
- Alteration includes but is not limited to apathy, disinhibition and confusion
- Consider subclinical seizures for significant alteration

APPENDIX D: MD ANDERSON SYMPTOM INVENTORY - BRAIN TUMOR (MDASI - BT)

Date: _____ Institution: _____
 Participant Initials: _____ Hospital Chart #: _____
 Participant Number: _____

MD Anderson Symptom Inventory - Brain Tumor (MDASI - BT)

Part I. How severe are your symptoms?

People with cancer frequently have symptoms that are caused by their disease or by their treatment. We ask you to rate how severe the following symptoms have been *in the last 24 hours*. Please select a number from 0 (symptom has not been present) to 10 (the symptom was as bad as you can imagine it could be) for each item.

	Not Present										As Bad As You Can Imagine	
	0	1	2	3	4	5	6	7	8	9	10	
1. Your pain at its WORST?												
2. Your fatigue (tiredness) at its WORST?												
3. Your nausea at its WORST?												
4. Your disturbed sleep at its WORST?												
5. Your feelings of being distressed (upset) at its WORST?												
6. Your shortness of breath at its WORST?												
7. Your problem with remembering things at its WORST?												
8. Your problem with lack of appetite at its WORST?												
9. Your feeling drowsy (sleepy) at its WORST?												
10. Your having a dry mouth at its WORST?												
11. Your feeling sad at its WORST?												
12. Your vomiting at its WORST?												
13. Your numbness or tingling at its WORST?												
14. Your weakness on one side of the body at its WORST?												
15. Your difficulty understanding at its WORST?												
16. Your difficulty speaking (finding the words) at its WORST?												

Date: _____ Institution: _____
 Participant Initials: _____ Hospital Chart #: _____
 Participant Number: _____

	As Bad As You Can Imagine										
	0	1	2	3	4	5	6	7	8	9	10
17. Your seizures at its WORST?											
18. Your difficulty concentrating at its WORST?											
19. Your vision at its WORST?											
20. Your change in appearance at its WORST?											
21. Your change in bowel pattern (diarrhea or constipation) at its WORST?											
22. Your irritability at its WORST?											

Part II. How have your symptoms interfered with your life?

Symptoms frequently interfere with how we feel and function. How much have your symptoms interfered with the following items *in the last 24 hours*? Please select a number from 0 (symptoms have not interfered) to 10 (symptoms interfered completely) for each item.

	Interfered Completely										
	0	1	2	3	4	5	6	7	8	9	10
23. General activity?											
24. Mood?											
25. Work (including work around the house)?											
26. Relations with other people?											
27. Walking?											
28. Enjoyment of life?											

Appendix E: STUDY PARTICIPANT SELF-ADMINISTRATION INSTRUCTIONS

DF/HCC

DANA-FARBER / HARVARD CANCER CENTER

Study Participant Self-Administration Instructions

The study staff will explain how to take the study drug, *ONC201*, but these are points to remember:

Patients will receive *ONC201* while in the clinic on day 1 of each cycle. They will take *ONC201* at home on days 8 and 15 of each cycle. The study drug, *ONC201*, will be supplied in capsule form for oral dosing.

Surgical Arm Patients must be evaluated in clinic prior to dosing at home for the first dose after surgery (i.e., the dose taken approximately one week post-surgery).

Patients should take the dose of *ONC201* specified by their physician 2 hours prior or 2 hours following food or a meal. **If the patient vomits after taking *ONC201*, they should not retake the dose. Missed doses will not be made up, if more than 3 days from the intended day of administration.**

ONC201 should be taken with a glass of water and consumed over as short a time as possible. Patients should swallow the capsules as a whole and not chew them. Do not crush or empty the capsule. If vomiting occurs during the course of treatment, no re-dosing of the patient is allowed before the next scheduled dose. The occurrence and frequency of any vomiting during a treatment cycle must be noted as an adverse event.

Please call your doctor or research nurse before taking any new prescription or over-the-counter medications/supplements other than the study drugs.

For any problems, issues, or questions you may have, please contact: _____

DF/HCC

DANA-FARBER / HARVARD CANCER CENTER

Study Participant Self-Administration Study Drug Diary

Please record how many capsules you take of *ONC201* the time you take them and any comments here below and bring the completed Diary as well as your study drug supply, including empty bottles, to every study visit. This will help us keep track of your study drug and how well you are tolerating it.

Participant Identifier: _____ Cycle Number: _____
 Protocol #: 15-318 ONC201 Assigned Dose: _____ mg
 Doctor: _____
 Nurse: _____

You will take the following number of _____ each time (per dose) as listed in the table below:

Study Drug Name	# of capsules (tablets) to take per time/dose	# of times/doses each day	Approximate time to take drug
ONC201			__:__  a.m.  p.m.

Week	Date	Number of ONC201 Capsules	Time of Dose
1			__:__  a.m. /  p.m.  Dose Not Taken Why: _____
2			__:__  a.m. /  p.m.  Dose Not Taken Why: _____
3			__:__  a.m. /  p.m.  Dose Not Taken Why: _____

Participant/Caregiver Signature: _____
 Date: _____

DF/HCC

DANA-FARBER / HARVARD CANCER CENTER

FOR STUDY TEAM USE ONLY	
Staff Initials:	
Date Dispensed:	Date Returned:
# pills/caps/tabs dispensed:	# pills/caps/tabs returned:
# pills/caps/tabs that should have been taken:	
Discrepancy Notes:

### 1. Introduction

This abbreviated Statistical Analysis Plan (SAP) describes the statistical analyses to be conducted for the Study ONC006. For simplicity, reference is made to existing Integrated Summary of Safety (ISS) and Integrated Summary of Efficacy (ISE) SAPs when approaches are the same.

Study ONC006 is a Phase II, open-label, multi-center clinical trial of ONC201 in adult

progressive/recurrent glioma with six arms. All subjects in Arm A receive oral ONC201 at 625 mg every 3 weeks and all subjects in Arms B, C, D, E, and F receive oral ONC201 at 625mg every week. Arms C and E include patients who have surgical resection of their tumor 1 day after the second (or more) dose of ONC201. All subjects remain on study until progressive disease, unacceptable toxicity or withdrawal of consent. For other study details, refer to the study protocol.

#### 2. General Conventions

The All Treated Analysis Set includes all patients who receive at least one dose of ONC201. This will be used for all analyses.

Unless otherwise specified, continuous variables will be summarized using descriptive statistics [number of observations, mean, standard deviation (SD), median,  $1^{st}(Q1)$  and  $3^{rd}(Q3)$  quartiles, minimum and maximum]. Categorical variables will be summarized as number (percent) of patients.

Day 1 is defined as the date of the first dose of study drug. For events that occur on or after Day 1, study day is defined as (date of event - date of Day 1 + 1). For events that occur prior to Day 1, study day is defined as (date of event - date of Day 1). There is no Day 0. Baseline is defined as the last observed measurement on or before the date of the first dose of study drug.

In general, other than for partial dates, missing data will not be imputed and will be treated as missing. Unless otherwise specified, partial dates will be imputed using the following rules:

- If year is missing, do not impute.
- If only day is missing, impute day as 1st of the month for start dates, end of the month for end dates, and 15th of the month for other dates.
- If day and month are missing, impute as January 1st for start dates, December 31st for end dates, and July 1st for other dates.

#### 3. Analyses

All analyses will be presented by Arm and for All Patients. Otherwise, specified patient disposition, study drug usage, prior/concomitant/post-ONC201 medications, demographic and baseline characteristics, adverse events, and laboratories will use methods and summaries defined in the ISS SAP.

Laboratory boxplots will be presented for all tests with at least 60 patients having numeric baseline results: one plot per test, time on the x-axis, value on the y-axis. The plots will not be broken out by arm (i.e. only the All Patients group). Only Baseline and Cycles 2-12 will be presented. For Cycles 2-12, nominal visits will be used; if multiple values are associated with a visit, the highest value will be used for chemistry tests and lowest value will be used for hematology tests.

The following efficacy analyses will be performed: best overall response, overall response rate, disease control rate, duration of response, progression-free survival, and overall survival. All analyses will be

based on the investigator-assessed overall RANO response. Discontinuation of treatment due to progressive disease will also be considered. All analyses, aside from overall survival, will be censored at the earlier of: (1) last disease assessment or (2) initiation of other anticancer therapy.

Cycle 1, 2 hour ONC201 plasma concentrations will be summarized descriptively.

Collected data contributing to presented tables and figures will be listed.

Other analyses specified in the protocol will either not be completed, or will be defined outside the scope of this plan.

Following is a complete list of the tables, figures, and listings to be prepared (with clarifying notes in parentheses).

Number	Description
Table 1.1	Patient Disposition
Table 1.2	Demographics and Baseline Characteristics
Table 1.3	Study Drug Usage
Table 1.4.1	Prior Medications
Table 1.4.2	Concomitant Medications
Table 1.4.3	Post-ONC201 Medications
Table/Figure 2.1	Progression-free Survival
Table/Figure 2.2	Overall Survival
Table 2.3	Response Rate (includes ORR, BOR, and DCR)
Table/Figure 2.4	Duration of Response
Table 3.x.1*	Treatment-emergent Adverse Events (TEAE)
Table 3.x.2*	TEAE Grade 3 and Above
Table 3.x.3*	Serious TEAE
Table 3.x.4*	TEAE Leading to Death
Table 3.x.5*	TEAE Leading to Study Drug Discontinuation, Reduction, or Interruption
Table 3.x.6*	Study Drug Related TEAE
Table 3.x.7*	Study Drug Related TEAE Grade 3 and Above
Table 3.x.8*	Study Drug Related Serious TEAE
Table 3.x.9*	Study Drug Related TEAE Leading to Death
Table 3.x.10*	Study Drug Related TEAE Leading to Study Drug Discontinuation, Reduction,
	or Interruption
Table 3.x.11*	TEAE by Maxium Severity (overall only)
Table 3.x.12*	Study Drug Related TEAE by Maximum Severity (overall only)
Table 4.x.1*	Graded Laboratory Results (maximum post-baseline)
Table 4.x.2*	Graded Treatment-emergent Laboratory Results (maximum post-baseline, result
	only counted if > Baseline Grade)
Table 5.1	Plasma Concentrations (Cycle 1, 2 hour only)
Figure 4.1	Boxplot of Laboratory Results
Listing 1.1	Patient Disposition
Listing 1.2	Demographics and Baseline Characteristics
Listing 1.3	Study Drug Usage
Listing 1.4	Other Medications
Listing 2.1	Efficacy Outcomes
Listing 3.1	Adverse Events
Listing 3.2	AE Leading to Death
Listing 3.3	AE Leading to Study Drug Discontinuation, Reduction, or Interruption
Listing 4.1	Listing of Graded Laboratory Results (includes all results for a patient/test where
	at least one post-baseline result is $\geq$ Grade 1)
Listing 5.1	Plasma Concentrations (Cycle 1, 2 hour only)
x=1: all post-baseline	e, x=2: prior to initiation of other anticancer therapy

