3. PARTICIPANT SELECTION

3.1 Eligibility Criteria

1. For Arms **A, B and C**: Histologically confirmed World Health Organization Grade IV glioblastoma.
For Arm **D**: Must have a WHO Grade IV glioma and the tumor must harbor a histone H3 K27M mutation detected in a Clinical Laboratory Improvement Amendment (CLIA) certified laboratory by immunohistochemistry or DNA sequencing test on any glioma tumor sample. The H3 K27M mutation is often reported as H3 K28M in gene sequencing assays.
For Arm **E**: Must have clinical and/or radiographic evidence of a midline glioma (involving the brainstem, thalamus, spinal cord, hypothalamus, basal ganglia, brainstem [non-DIPG], cerebellum, cerebellar peduncle, midline cortex, corpus collosum, pineal region, optic tract, or optic chiasm), and be eligible for salvage surgical resection as deemed by the site Investigator.
For Arm **F**: Must have a diffuse midline glioma involving the brainstem, thalamus or spinal cord, without the H3 K27M mutation or with unknown H3 mutation status at the time of enrollment.
2. Unequivocal evidence of progressive disease on contrast-enhanced brain CT or MRI as defined by RANO-HGG Criteria, or have documented recurrent glioblastoma or WHO Grade IV glioma on diagnostic biopsy. For Arm E, patients are not required to have evidence of recurrent disease for inclusion.
3. Previous first line therapy with at least radiotherapy and temozolomide. For patients with tumors that exhibit unmethylated MGMT promoter, prior treatment with temozolomide is not required. For Arms D, E, and F, previous first line therapy with at least radiotherapy.
4. For Arm A or D: Any number of recurrences are allowable.
For Arm B: First recurrence (only) WHO Grade IV glioma. First recurrence is defined as progression following initial therapy (i.e., radiation \pm chemotherapy). For participants who had prior therapy with radiation or chemotherapy for a low-grade glioma, the surgical diagnosis of a high-grade glioma will be considered the first recurrence. For patients who did not get additional treatment following surgery and diagnosis of low-grade glioma, surgical diagnosis of high-grade glioma will not be considered the first recurrence. Instead, progression after treatment will be considered first recurrence.
For Arm C: Patients must have clinical and/or radiographic evidence of first recurrence of glioblastoma and be eligible for salvage surgical resection as deemed by

the site Investigator.

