For Arm E: Recurrent disease is not required. Patients must have a midline glioma (defined as a glioma involving the pons, thalamus, spinal cord, hypothalamus, basal ganglia, brainstem [non-DIPG], cerebellum, cerebellar peduncle, midline cortex, corpus collosum, pineal region, optic tract, or optic chiasm), and be eligible for salvage surgical resection as deemed by the site Investigator.

5. Interval of at least 90 days from the completion of radiotherapy to the first dose of ONC201. If patients are within 90 days of radiotherapy, then the progressive lesion must be outside of the high-dose radiation target volume or have unequivocal evidence of progressive tumor on a biopsy specimen.
6. From the projected start of scheduled study treatment, the following time periods must have elapsed: 5 half-lives from any investigational agent, 4 weeks from cytotoxic therapy (except 23 days for temozolomide and 6 weeks from nitrosoureas), 6 weeks from antibodies, or 4 weeks (or 5 half-lives, whichever is shorter) from other anti-tumor therapies.
7. All adverse events Grade > 1 related to prior therapies (chemotherapy, radiotherapy, and/or surgery) must be resolved, except for alopecia.
8. Male or Female age ≥ 16 years.
9. Karnofsky Performance Status (KPS) ≥ 60 (see Appendix A).
10. Adequate organ and marrow function as defined below, all screening labs should be performed within 14 days of treatment initiation:
 - leukocytes $\geq 3,000/\text{mcL}$
 - absolute neutrophil count $\geq 1,500/\text{mcL}$
 - platelets $\geq 100,000/\text{mcL}$
 - hemoglobin $> 8.0 \text{ g/dL}$
 - total bilirubin $\leq 2.0 \times$ upper limit of normal
 - AST (SGOT)/ALT (SGPT) $\leq 2.5 \times$ upper limit of normal
 - creatinine \leq upper limit of normal
 - OR
 - creatinine clearance $\geq 60 \text{ mL/min/1.73 m}^2$ for patients with creatinine levels above normal.
11. CT or MRI within 14 days prior to start of study drug.
12. Corticosteroid dose must be stable or decreasing for at least 5 days prior to the baseline CT or MRI scan. For Arm B: Corticosteroid dose must be stable or decreasing for at least 2 weeks prior to study entry.
13. The effects of ONC201 on the developing human fetus are unknown. For this reason,

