Intratumoral ONC201 concentration in patients with recurrent GBM will be summarized using descriptive statistics separately for Arm C and E separately. A sample size of 6 achieves 80% power to detect a difference of -1.4 between the null hypothesis mean of 0.0 and the alternative hypothesis mean of 1.4 with an estimated standard deviation of 1.0 and with a significance level (alpha) of 0.05000 using a two-sided one-sample t-test. We are looking for an effect size of 2.9 since the target threshold for intratumoral drug concentrations is 2.9 uM representing the IC50 of ONC201 in cancer cell panels profiled for in-vitro efficacy.

Below you will find a table with calculations of minimal effect size corresponding to differing SDs for a sample size of 6 patients at 80% power and a two sided alpha of 0.5.

Power	N	Alpha	Beta	Mean0	Mean1	S	Effect Size
0.80000	6	0.05000	0.20000	0.0	1.4	1.0	1.435
0.80000	6	0.05000	0.20000	0.0	1.5	1.0	1.435
0.80000	6	0.05000	0.20000	0.0	1.6	1.1	1.435
0.80000	6	0.05000	0.20000	0.0	1.7	1.2	1.435
0.80000	6	0.05000	0.20000	0.0	1.8	1.3	1.435
0.80000	6	0.05000	0.20000	0.0	1.9	1.3	1.435
0.80000	6	0.05000	0.20000	0.0	2.0	1.4	1.435
0.80000	6	0.05000	0.20000	0.0	2.1	1.5	1.435
0.80000	6	0.05000	0.20000	0.0	2.2	1.5	1.435
0.80000	6	0.05000	0.20000	0.0	2.3	1.6	1.435
0.80000	6	0.05000	0.20000	0.0	2.4	1.7	1.435
0.80000	6	0.05000	0.20000	0.0	2.5	1.7	1.435
0.80000	6	0.05000	0.20000	0.0	2.6	1.8	1.435
0.80000	6	0.05000	0.20000	0.0	2.7	1.9	1.435
0.80000	6	0.05000	0.20000	0.0	2.8	2.0	1.435
0.80000	6	0.05000	0.20000	0.0	2.9	2.0	1.435

References

Zar, Jerrold H. 1984. Biostatistical Analysis (Second Edition). Prentice-Hall. Englewood Cliffs, New Jersey.

Report Definitions

Power is the probability of rejecting a false null hypothesis. It should be close to one.
N is the size of the sample drawn from the population. To conserve resources, it should be small.
Alpha is the probability of rejecting a true null hypothesis. It should be small.
Beta is the probability of accepting a false null hypothesis. It should be small.
Mean0 is the value of the population mean under the null hypothesis. It is arbitrary.
Mean1 is the value of the population mean under the alternative hypothesis. It is relative to Mean0.
Sigma is the standard deviation of the population. It measures the variability in the population.

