13.3 Statistical Methods for Efficacy Analyses

Efficacy analyses will be performed separately for each arm. Subgroup analyses of the primary tumor location within the brain (e.g. thalamus) and the H3 K27M mutation will be performed across all cohorts. For PFS and OS endpoints, Kaplan-Meier (KM) curves and median estimates from the KM curves will be provided as appropriate. Subjects without efficacy evaluation data or without survival data will be censored at Day 1, as appropriate. Participants without measurable disease will not be included in the analysis of ORR.

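### Arm E may enrol patients without recurrence, but the pooled efficacy summaries and cross-cohort subgroups do not separate them from recurrent patients

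*SAP*

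**What the plan says.** **Entry.** Protocol 3.1, criterion 2, asks for unequivocal progression on imaging or a biopsy-documented recurrence, and then makes one exception: "For Arm E, patients are not required to have evidence of recurrent disease for inclusion". Criterion 4 repeats it: "For Arm E: Recurrent disease is not required". No other arm is exempt. Criterion 1 places every Arm E tumour in a midline structure. On prior treatment, criterion 3 reads "For Arms D, E, and F, previous first line therapy with at least radiotherapy", and criterion 5 sets an "Interval of at least 90 days from the completion of radiotherapy to the first dose of ONC201", with exceptions only for patients whose progression lies outside the high-dose field or is proven on biopsy.

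**Population label.** The primary objective (Protocol 1.2) concerns recurrent glioblastoma or recurrent Grade IV glioma. The SAP introduction describes the trial as one in adult "progressive/recurrent glioma with six arms". Protocol 13.1 says "Intratumoral ONC201 concentration in patients with recurrent GBM will be summarized using descriptive statistics separately for Arm C and E", although Arm E requires neither recurrence nor glioblastoma.

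**Analysis.** SAP Section 2 uses one set, everyone who received a dose, for all analyses. SAP Section 3 says "All analyses will be presented by Arm and for All Patients", and its efficacy list covers best response, ORR, DCR, duration of response, PFS and OS. It mentions no flag, stratum or exclusion for recurrence status. Protocol 13.3 keeps efficacy separate by arm but adds: "Subgroup analyses of the primary tumor location within the brain (e.g. thalamus) and the H3 K27M mutation will be performed across all cohorts". Protocol 13.1 also allows patients from other arms with a known H3 K27M mutation into the Arm D analyses, with no condition on recurrence.

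**The concern.** A patient dosed after progression and a patient dosed after first-line radiotherapy without progression are at different stages of disease when the clock starts. Criterion 5 sharpens the contrast. Its exceptions all need progression, so a non-recurrent Arm E patient must be at least 90 days past radiotherapy and is selected for having stayed progression-free. A pooled PFS or OS curve labelled as recurrent glioma would then describe a mixture whose composition is not reported.

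The subgroups carry a second problem. Non-recurrent patients can come only from Arm E, and all Arm E tumours are midline. In a cross-cohort comparison, an apparent effect of midline or thalamic location could partly reflect earlier disease stage. The same could happen for H3 K27M status if mutated tumours are over-represented in Arm E, but the documents do not say whether they are.

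**Working it through.** **The plan's own figure.** Protocol 13.1 gives 84% power for 30 patients, null PFS-6 0.10 against 0.30, one-sided exact test at 0.05. At least 6 successes of 30 has size 0.073, which is too large. At least 7 of 30 has size 0.0258 and power 0.8405. The stated 84% reproduces, and this rule is used for Arm D below.

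**Time origin.** Protocol 13.1 counts PFS from the start of study therapy, and SAP Section 2 sets Day 1 at first dose. Both apply to every arm. No separate OS origin is stated beyond the SAP's Day 1 convention. So there is one origin, with disease state at that origin mixed.

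**Arm E's share of All Patients.** Inputs: Arms A, B, D and F at 16–30 each (Protocol 1.1); Arm C 6, up to 12 enrolled; Arm E 12, up to 18 enrolled (Protocol 13.1).
- Minimum throughout: 12/(4×16 + 6 + 12) = 12/82 = 14.6%
- Maximum throughout: 18/(4×30 + 12 + 18) = 18/150 = 12.0%
- Smallest Arm E, largest others: 12/(4×30 + 12 + 12) = 12/144 = 8.3%
- Largest Arm E, smallest others: 18/(4×16 + 6 + 18) = 18/88 = 20.5%

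Arm E does not exclude recurrent patients, so each figure is an upper bound on the non-recurrent share.

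**Effect on a pooled PFS-6.** Assumptions, none from the documents: PFS-6 is 0.10 in all other patients, every Arm E patient is non-recurrent, and their PFS-6 is q = 0.30 to 0.50. With share s, pooled PFS-6 = 0.10 + s(q − 0.10).

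| Share s | q = 0.30 | q = 0.50 |
|---|---|---|
| 14.6% | 0.129 | 0.159 |
| 12.0% | 0.124 | 0.148 |
| 8.3% | 0.117 | 0.133 |
| 20.5% | 0.141 | 0.182 |

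If q = 0.10 there is no distortion.

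**Inside a midline-type subgroup (illustration).** Suppose such a subgroup were Arms D, E and F only. The documents do not fix its make-up, and Arm D entry is not restricted by location.
- Like for like, Arm E would be 12/(2×16 + 12) = 12/44 = 27.3%, or 18/(2×30 + 18) = 18/78 = 23.1%.
- At the extremes it would be 12/72 = 16.7% or 18/50 = 36.0%.
- On the same assumptions the subgroup would read from 0.10 + 0.167×0.20 = 0.133 to 0.10 + 0.36×0.40 = 0.244.

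**Arm D additions.** Suppose k of the 30 patients analysed in Arm D are non-recurrent with PFS-6 of 0.30–0.50, and the rest are at the null of 0.10. The exact chance of at least 7 of 30 is:

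| k | Chance of crossing the bar |
|---|---|
| 0 | 0.026 |
| 2 | 0.045–0.068 |
| 4 | 0.072–0.148 |
| 6 | 0.110–0.272 |

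If six such patients were added to 30 instead, the rule becomes at least 8 of 36 (size 0.024), and the chance is 0.093–0.225. The protocol does not say which reading applies, and the number of eligible Arm E patients is unknown.

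**The case against.** The strongest reply is that nothing decisive rests on the pooled column. It is descriptive, no test on All Patients is planned, and Arm E has its own column beside it. The pool is also mixed in other ways: two dosing schedules, first versus any recurrence, glioblastoma versus midline glioma, and prior bevacizumab barred or allowed. Taking out non-recurrent patients would not make it a clean population. All of that stands and limits the weight of the point. It does not remove the mismatch between the population label and who may enter Arm E.

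The subgroup part is also limited. The SAP's complete list of outputs contains no location or H3 K27M analysis, and unlisted protocol analyses are either dropped or defined elsewhere. Protocol 13.3 names no test. Arm F enrols only midline tumours and is not exempt from criterion 2, so a midline subgroup would not rest on Arm E alone.

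A reader might infer three stronger things:
- **That PFS and OS are measured from two different origins.** They are not. PFS runs from the start of therapy in every arm, and the SAP has one Day 1.
- **That the pooled estimate is known to overstate outcome in recurrent glioma.** The documents give no PFS-6 for non-recurrent patients and no count of them. The 9–11% history is for recurrent glioblastoma, not for every other arm.
- **That the intratumoral concentration results are compromised.** The label in Protocol 13.1 is a wording slip. Arms C and E are summarised separately, and the SAP lists no such output.

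**Conclusion.** The point holds as a gap in labelling and stratification. Arm E can contribute non-recurrent patients to summaries presented as progressive or recurrent glioma, and no planned output shows how many there are or how they did. Arm E is about 12–15% of All Patients like for like (8.3–20.5% at the extremes), which caps the non-recurrent share. Under the stated outside assumptions a true 10% PFS-6 would read about 12–16%, or 12–18% at the extremes. The effect would be zero if non-recurrent patients did no better.

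Results by arm are not altered by the pooling. The one route to a tested result is Protocol 13.1's allowance for H3 K27M patients from other arms to join Arm D, whose PFS-6 is set against a 10% null drawn from recurrent glioblastoma. That route is permissive, and its size depends on a number the documents do not give. The change is worth making because it is cheap, not because a planned conclusion is shown to be wrong.

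**What to change.** - **Flag.** Derive recurrent or progressive at entry (yes/no) for every treated patient. Criterion 2 does not apply to Arm E, so eligibility data alone may not record it. Use the imaging history and the radiology or pathology reports required by Protocol 5.2 and the Study Calendar.
- **SAP Section 3, Tables/Figures 2.1–2.4.** Keep All Patients as it is, consistent with the All Treated set. Add a pooled column restricted to patients recurrent or progressive at entry, and show Arm E by the flag.
- **Protocol 13.3.** Restrict the location and H3 K27M subgroups to flagged patients, or stratify by the flag, wherever those analyses end up being defined.
- **Protocol 13.1, Arm D.** State that patients from other arms join the Arm D analyses only if flagged as recurrent at entry, and whether they add to or count within the 30.
- **Wording.** In the SAP introduction, note that Arm E does not require recurrence. In Protocol 13.1, describe Arm E concentrations as from midline glioma, recurrent or not. State the OS origin.

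Cost: some text in both documents, derivation work for one variable, and a recurrent-only pooled set with up to 18 fewer patients. Safety tables stay pooled.
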